1.2.4 Summary

We have a compelling rationale for combining Ipilimumab and SBRT with Nivolumab for metastatic MCC with our preliminary data suggesting a potential abscopal effect of radiation therapy in MCC potentiated by Ipilimumab, and expression of PD-L1 in the majority of MCC patients. Poor prognosis associated with metastatic MCC requires development of a new and effective therapeutic modality.

Therefore, we propose to further augment the therapeutic efficacy of PD1 blockade in patients with metastatic Merkel cell carcinoma by the abscopal effect of stereotactic body radiation therapy (SBRT) and another immune checkpoint inhibitor, ipilimumab to boost immune priming. The optimal sequences of immunotherapy to partner with SBRT to maximize the efficacy of combined treatment remain elusive, and this study will allow for direct comparison of the clinical benefit, as measured by objective response rate, provided by the addition of SBRT to nivolumab and ipilimumab in MCC.

Finally, the proposed clinical trial is strategically designed to define the standard treatment regimens for metastatic Merkel cell carcinoma with acceptable toxicity. The insights on the synergy of SBRT, Nivolumab and Ipilimumab drawn from Merkel cell carcinoma will be applicable to other solid cancers.

1.3 Objectives(s)

1.3.1 Primary Objectives

- To compare the efficacy, as measured by ORR, provided by nivolumab and ipilimumab versus

SBRT plus nivolumab and ipilimumab in subjects with metastatic Merkel cell carcinoma.

1.3.2 Secondary Objectives

- To compare the progression free survival (PFS) of nivolumab and ipilimumab versus SBRT plus nivolumab and ipilimumab in subjects with metastatic Merkel cell carcinoma.
- To compare the overall survival (OS) of nivolumab and ipilimumab versus SBRT plus nivolumab and ipilimumab in subjects with metastatic Merkel cell carcinoma.
- To evaluate the local control of irradiated tumor provided by SBRT in combination with nivolumab and ipilimumab
- To assess the overall safety and tolerability of nivolumab and ipilimumab versus SBRT plus nivolumab and ipilimumab in subjects with metastatic Merkel cell carcinoma.
- To evaluate whether PD-L1 expression is a predictive biomarker for ORR;
- To evaluate the Health Related Quality of Life (HRQoL) as assessed by European Organisation for Research and Treatment of Cancer (EORTC) QLQ-C30.

1.3.3 Exploratory Objectives

- To evaluate associations between Merkel polyomavirus expression status and clinical efficacy (ORR, PFS and overall survival (OS))
- To explore potential biomarkers associated with clinical efficacy (ORR, PFS, and OS) and/or incidence of adverse events by analyzing biomarker measures within the tumor microenvironment and periphery (eg, blood, serum, plasma and PBMCs) in comparison to clinical outcomes
- To assess changes in health status and work and activity impairment in treatment groups using the EuroQol EQ-5D and the Work Productivity and Activity Impairment questionnaire (WPAI:GH), respectively.

1.4 Rationale for Study Design

1.4.1 Rationale for Studying Merkel Cell Carcinoma

Merkel cell carcinoma is a rare cutaneous malignancy of neuroendocrine origin, which typically occurs in elderly patients in areas of the body with frequent sun exposure including the head and neck.^{1, 2} Merkel cell carcinoma also has a higher incidence in the severely immunosuppressed population, and has recently been found to be associated with infection by the Merkel cell polyomavirus.^{3,4} The incidence of MCC is estimated to be approximately 0.3–0.6/100,000 in the US, and it appears to have been increasing over the last few decades³¹.

Merkel cell carcinoma is perhaps the most aggressive and lethal primary skin cancer, with a high rate of locoregional recurrence and the majority of patients die from distant metastasis. Survival rates at 5 years range from 23-80%.⁵⁻⁹ Despite the poor prognosis, the rarity of this cancer has limited conducting prospective, randomized data guiding to guide treatment. Combined with aggressive behavior of this cancer refractory to most systemic agents, it has been difficult to define the standard of care in MCC.

Treatment of non-metastatic Merkel cell carcinoma typically includes wide excision with 1-2 cm

margins with a sentinel lymph node biopsy¹⁰⁻¹⁴. Given the high risk of locoregional recurrence following surgery alone, adjuvant radiation therapy (RT) is typically recommended.

Treatment of metastatic MCC has been a clinical challenge and limited options, such that until recently, palliative approach to the management of these patients was acceptable. First-line treatment typically involved platinum based chemotherapy etoposide, and the second line chemotherapy included irinotecan, topotecan and weekly paclitaxel. Surgery and radiation therapy are palliative modalities in metastatic MCC. Unfortunately, the response rate to systemic chemotherapy was low with poor durability of responses.

Therefore, alternative approaches for treatment of MCC have been pursued in recent years including targeted biotherapy. A phase II trial of imatinib, based on high expression of KIT in MCC, demonstrated median progression-free survival at 1 month and 1 year overall survival rate at 17%³². Another multi-tyrosine kinase inhibitor, cabozantinib targeting c-met is being tested in a phase II trial. However, promising breakthrough for metastatic MCC came through immunotherapy.

1.4.2 Immunotherapy in Merkel Cell Carcinoma

The concept of cancer immunotherapy for MCC is based on several key aspects of this particular cancer. First, MCC is a viral-associated cancer expressing viral antigens. Because viral proteins represent non-self antigens not encountered in thymus, central tolerance mechanisms are not anticipated for these antigens. Furthermore, prior studies have shown that patients indeed generate adaptive immune response against Merkel viral T antigen, which correlate with tumor load^{33,34}. Interestingly, high antibody titers for VP1 appear to have prognostic significance with improved progression-free survival³³. Improved prognosis was also observed with increased CD8 tumor-infiltrating lymphocytes³⁵.

There are several on-going clinical trials to harness immunogenicity of MCC. One effort is a phase I/II clinical trial utilizing MCPyV-reactive autologous T cell therapy for metastatic MCC (NCT01758458). Other studies also include intratumoral injection of IL-12 (NCT01440816) or TLR-4 agonist targeting antigen presenting cells to boost anti-tumoral immunity. A phase II cell-based immunotherapy utilizing neukoplast (NK-92) (NCT02465957) is also on-going. However, PD-L1/PD1 axis appears to be the most promising target for cancer immunotherapy in MCC with an excellent response rate.

1.4.3 Rationale for ORR as Primary Endpoint with PFS and OS as a Secondary Endpoint

The intention of this trial is to ascertain the clinical responses of MCC to different combinations of SBRT and immune checkpoint inhibitors, nivolumab and ipilimumab, in metastatic patients. The rate of overall response, complete response and partial response of target lesions will be most sensitive in detecting the incremental benefit from the addition of SBRT and/or ipilimumab to PD1 blockade alone. Larger patient cohorts in each arm will be required to achieve statistical power detect the differences in survival outcomes, PFS and OS, which is not feasible in MCC.

1.4.4 Rationale for Two Experimental Arm Design

Merkel cell carcinoma is a rare malignancy with the incidence estimated to be approximately 0.3–0.6/100,000 in the US³¹. Merkel cell carcinoma is associated with a high rate of locoregional recurrence and the majority of patients die from distant metastasis. Survival rates at 5 years range from 23-80%.⁵⁻⁹ Despite the poor prognosis, the rarity of this cancer has limited conducting prospective,

randomized data guiding to guide treatment. Combined with aggressive behavior of this cancer refractory to most systemic agents, it has been a clinical challenge to define the standard of care in MCC. Most recently, a promising breakthrough for metastatic MCC came through PD1/PDL1 axis blockade^{36,37}. Despite excitement elicited by high response rate to PD1 blockade for metastatic MCC, further optimization to maximize the benefit of immunotherapy is of pivotal importance in this perhaps most aggressive and lethal skin cancer.

Therefore, we propose a randomized phase II trial in which both arms of the trial are experimental. By employing carefully designed two arm Simon's two stage design, we will compare both experimental arms with the historical control as well as each other. Preclinical and clinical evidence extrapolated from other solid malignancies including melanoma suggests improved therapeutic efficacy with acceptable additional toxicity in both proposed experimental arms. Such clinical trial design is not unprecedented. Indeed, even in NRG-HN002 trial, a randomized phase II trial for patients with p16 positive, non-smoking associated, locoregionally advanced oropharyngeal cancer (NCT02254278), a two arm experimental design has been used to expedite optimization of clinical decision making for this relatively common disease entity. Given the rarity of this cancer and absence of standard of care with acceptable therapeutic efficacy, a two experimental arm design is justified.

1.4.5 Rationale for the Dose and Schedule for Nivolumab

Nivolumab was chosen as one of the experimental drugs because of a favorable risk-benefit ratio as seen in the large Phase 1 CA209003³⁸. Additionally, other Phase 2 and 3 studies in the nivolumab development program use this dose and regimen. The dose and schedule of nivolumab in this study will be 240 mg every two weeks, which is equivalent to 3mg/kg every two weeks, based upon the analyses of safety, efficacy, and exposure-response data from the Phase 1 study CA209003. Anti-tumor activity was observed at dose levels ranging from 1 to 10 mg/kg in melanoma, NSCLC, and RCC, as well as at dose levels of 0.1 and 0.3 mg/kg in melanoma. The anti-tumor activity of nivolumab in RCC was investigated at dose levels 1 and 10 mg/kg, with the higher activity observed at 10 mg/kg. The observed anti-tumor activity in melanoma, and NSCLC was highest at 3 mg/kg, suggesting that anti-tumor activity approaches a plateau at dose levels of 3 mg/kg and above. Consistent with these observations, the results of the exposure-response analyses for these tumor types show that the probability of a tumor response tended to approach a plateau for trough concentrations produced by 3 and 10 mg/kg every 2 week dosing.

Nivolumab was adequately tolerated up to 10 mg/kg, the highest dose level tested, and no MTD was identified. Although the spectrum, frequency, and severity of nivolumab-related AEs were generally similar across the dose levels tested, the 10 mg/kg doses level had numerically higher Grade 3/4 drug-related SAEs and AEs leading to discontinuation. Therefore, most prior clinical trials employed nivolumab dose of 3 mg/kg Q2W. More recently, a flat dose of 240 mg Q2W has been shown to have comparable efficacy and toxicity while simplifying dosing strategy. Therefore, based upon the totality of the safety, efficacy, and exposure-response data, a flat dose of 240 mg Q2W was selected as the dose anticipated to achieve an appropriate balance of efficacy and risk.

1.4.6 Rationale for the Dose and Schedule for SBRT

Studies have demonstrated that SBRT for ablative treatment of non-symptomatic, solitary metastases is technically feasible. A high rates of in-field cancer control is achieved with acceptable toxicity.

The rationale for this dose fractionation opposed to conventional radiation therapy or higher radiation dose is several fold. Preclinical studies have demonstrated that high dose per fraction appears to be

most immunogenic^{22,23} leading to immune activation. At this higher dose per fraction, a more conformal treatment delivered through SBRT is necessary for safety. Moreover, by completing radiation therapy in fewer fractions, we can avoid repeated irradiation to the tumor infiltrating lymphocytes, which will render them ineffective. Also, conformal radiation therapy offered by SBRT will spare lymphoid tissues where the immune synapse occurs during priming. While definitive and adjuvant radiation therapy for MCC has traditionally involved a prolonged course of radiation therapy with wider radiation field, a recent study demonstrates that a single fraction of 8Gy radiation therapy offers durable palliation in MCC²⁴. Therefore, a more conformal treatment delivered through SBRT is more appropriate in the metastatic setting as a modality for systemic immune activation while providing local control benefit with minimal acute and long-term toxicities.

Also of note, most disease sites can be treated safely to a dose far exceeding the proposed dose in this clinical trial. However, the intent of higher ablative dose of SBRT is maximal local control in placement of surgical approach with acceptable toxicity. Contrarily, the primary goal of SBRT in this clinical trial is to induce immune activation. Therefore, we will limit our dose to 24Gy in 3 fractions. This dose fractionation can be safely delivered in most disease sites with minimal toxicity with anticipated durable local responses in Merkel cell carcinoma²⁴. More importantly, preclinical studies have demonstrated superior immunogenicity with this fractionation over a higher ablative dose in a single fraction secondary to regulatory T cell recruitment associated with higher radiation dose^{22,23}. In the absence of clinical evidence that an alternative dose fractionation is equivalent or superior, 24Gy delivered in 3 fractions is deemed optimal to exploit the abscopal effect of radiation therapy.

SBRT will be delivered the week following initiation of nivolumab and ipilimumab. Because immune activation by SBRT is by augmenting immune priming by release of tumor antigen and damage-associated molecular pattern¹⁵, SBRT was deliberately scheduled to follow ipilimumab to ensure that CTLA-4 blockade is already present at the time of delivery of SBRT. PD1 blockade has been one of the major pathways for T cell tolerance or exhaustion. PD-1 and PD-L1 have been shown to be up-regulated immediately following ionizing radiation in a preclinical murine model suggesting the potential role of this tolerance axis in suppressing immunogenicity of SBRT¹⁶ (Fig 3). Therefore, nivolumab will also be initiated the week prior to SBRT.

1.4.7 Rationale for the Dose and Schedule for Ipilimumab

In MDX010-20 (metastatic or unresectable setting), the ipilimumab monotherapy arm was administered 3 mg/kg ipilimumab every 3 weeks for four doses with acceptable toxicity. However, in combination with nivolumab, 3 mg/kg of ipilimumab elicited significant toxicity in Checkmate-067 trial for metastatic melanoma despite improved objective response rate with over 50% of patients unable to complete the study drugs in the combined arm³⁹. Subsequently, a number of clinical trials testing combination of nivolumab and ipilimumab adopted lower dose of ipilimumab with acceptable toxicity profiles while retaining improved efficacy²⁸. Of particular note, Checkmate-012 study has demonstrated ipilimumab at 1mg/kg Q6W in combination with nivolumab 3mg/kg Q2W is safe with significantly improved efficacy in comparison to nivolumab alone⁴⁰. This combination regimen is also being used for Checkmate-358 study, which includes patients with metastatic Merkel cell carcinoma. Therefore, we will utilize ipilimumab at 1 mg/kg Q6W in combination with nivolumab in this trial.

1.4.8 Rationale for Treating until Progression, Unacceptable Toxicity, or Withdrawal of Consent

Throughout the nivolumab and/or ipilimumab development program, most protocols have dosed until progression, unacceptable toxicity, or withdrawal of consent in the metastatic setting. In the absence of

dose-limiting toxicity, the treatment duration for metastatic cancer in many prior trials was usually not restricted. However, these therapeutic agents also come with toxicity. For instance, despite the protocol specified treatment duration of 3 years in EORTC 18071⁴¹ the median number of doses received for subjects in the ipilimumab arm was 7, corresponding to approximately 1 year duration of treatment. Additionally, there was a large decline in subjects still receiving dosing at the end of induction as compared to those still receiving dosing at the end of 1 year⁴². Furthermore 48.8% of subjects in the ipilimumab arm discontinued treatment due to adverse events related to study drug.

It should be also noted that the combination of both nivolumab and ipilimumab is associated with significantly increased toxicity. In the double-blind, multicenter phase 3 trial (CheckMate 067)²⁵ testing the safety and efficacy of nivolumab plus ipilimumab versus nivolumab and ipilimumab monotherapies, a significant increase in toxicity was seen in the combination group: grades 3–4 adverse events occurred in 55 % of patients, compared to 16.3 % in patients treated with nivolumab alone, and 27.3 % of patients treated with ipilimumab. Treatment-related adverse events leading to therapy discontinuation occurred in 36.4, 7.7, and 14.8 % of patients, respectively (most commonly diarrhea, fatigue, and pruritus).

Therefore, in order to minimize toxicity leading to discontinuation of study drug while maintaining efficacy of either study drug, ipilimumab is limited to 4 doses while nivolumab will continued until progression, unacceptable toxicity or withdrawal of consent.

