**A Phase 2, Randomized, Multi-institutional Study of Nivolumab and Ipilimumab
versus Nivolumab, Ipilimumab and Stereotactic Body Radiation Therapy for
Metastatic Merkel Cell Carcinoma**

NCT03071406

Version 11

January 26, 2023

Clinical Protocol

A Phase 2, Randomized, Multi-institutional Study of Nivolumab and Ipilimumab versus Nivolumab, Ipilimumab and Stereotactic Body Radiation Therapy for Metastatic Merkel Cell Carcinoma

PI: [name], PhD

Co-PI: [name]

Co-Investigator: [name]

Co-Investigator: [name], PhD

Co-Investigator: [name]

Co-Investigator: [name]

Co-Investigator: [name]

Co-Investigator: [name], PhD

Biostatistician: [name]

Pathologist: [name]

Radiologist: [name]

OSU Site PI: [name]

Collaborating Institutions:

Ohio State University James Cancer Hospital and Solove Research Institute

DOCUMENT HISTORY

Document	Date of Issue	Summary of Change
Original Protocol		Not applicable

SYNOPSIS

Clinical Protocol

Protocol Title: A Phase 2, Randomized, Multi-institutional Study of Nivolumab and Ipilimumab versus Nivolumab, Ipilimumab and Stereotactic Body Radiation Therapy for Metastatic Merkel Cell Carcinoma.

Investigational Product(s), Dose and Mode of Administration, Duration of Treatment with Investigational Product(s):

Stereotactic Body Radiation Therapy 24Gy in 3 fractions.

Nivolumab 240 mg/dose IV q2 weeks.

Ipilimumab 1 mg/kg/dose IV q6 weeks.

Treat subjects until disease progression, unacceptable toxicity or subject withdrawal of consent.

Study Phase: 2

Research Hypothesis: Treatment with nivolumab and ipilimumab, or nivolumab and ipilimumab in combination with stereotactic body radiation therapy (SBRT) will improve objective response rate as compared to nivolumab alone historical control in subjects with metastatic Merkel cell carcinoma.

Objectives:

Primary:

- To compare the efficacy, as measured by objective response rate (ORR), provided by nivolumab plus ipilimumab with or without SBRT in subjects with metastatic Merkel cell carcinoma.

[figure not shown]
Secondary:

- To compare the progression free survival (PFS) of nivolumab and ipilimumab versus SBRT plus nivolumab and ipilimumab in subjects with metastatic Merkel cell carcinoma.
- To compare the overall survival (OS) of nivolumab and ipilimumab versus SBRT plus nivolumab and ipilimumab in subjects with metastatic Merkel cell carcinoma.
- To evaluate the local control of irradiated tumor provided by SBRT in combination with nivolumab and ipilimumab

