- To assess the overall safety and tolerability of nivolumab and ipilimumab versus SBRT plus nivolumab and ipilimumab in subjects with metastatic Merkel cell carcinoma.
- To evaluate whether PD-L1 expression is a predictive biomarker for ORR.
- To evaluate the Health Related Quality of Life (HRQoL) as assessed by European Organisation for Research and Treatment of Cancer (EORTC) QLQ-C30.

Exploratory: See [Section 1.3.3](#) of the protocol.

Study Design:

This is a Phase 2, randomized, multi-institutional study of nivolumab and ipilimumab alone versus in combination with SBRT for subjects (≥ 18 years) with metastatic Merkel Cell Carcinoma. Approximately 50 subjects will be randomized 1:1 and stratified by prior immunotherapy exposure. Dose reductions will not be allowed.

Treatment Arms:

Randomized 1:1 [Arm A: Arm B]: Treatment until progression on either arm.

Arm A:

Nivolumab 240 mg IV over 30 min q2 weeks and Ipilimumab 1 mg/kg IV over 30 min q6 weeks until progression or unacceptable toxicity

Arm B:

Nivolumab 240 mg IV over 30 min q2 weeks and Ipilimumab 1 mg/kg IV over 30 min q6 weeks until progression or unacceptable toxicity

Radiation to be given at the start of week 2

- 8 Gy x3 doses in over ≤ 2 weeks

SBRT should begin the week following the first dose of nivolumab and ipilimumab. All sites other than skin should receive SBRT in consecutive days. Skin lesions can be treated every other day.

The number of lesions receiving SBRT will be at the treating physician's discretion based on anticipated toxicity. Larger or symptomatic lesions are of higher priority for SBRT. At least one target lesion will not receive SBRT, to evaluate ORR. The scatter radiation dose to this target lesion should be monitored if located less than 6cm from the irradiated lesions.

All subjects will be treated until progression of disease, unacceptable toxicity, or subject withdrawal of consent. Palliative radiation therapy will not be permitted while being treated under the protocol. The need for palliative radiation therapy will be considered progressive disease.

Study Population: Metastatic Merkel cell carcinoma subjects

Key Inclusion Criteria:

- At least 18 years of age
- ECOG PS < 2
- Active disease measurable by CT or MRI.
- Prior chemotherapy or immunotherapy will be allowed if new or persistent measurable site(s) of disease are present.
- Prior radiation therapy will be allowed if there is active measurable disease burden.

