4 INVESTIGATIONAL PLAN

4.1 Study Design and Duration

The study design schematic is presented in Figure 3.1-1.

Figure 4.1-1: Study Design Schematic

The subjects will be treated in both arms until disease progression, unacceptable toxicity, or subject withdrawal of consent.

This study will consist of three phases: screening, treatment, and follow-up. For a complete list of study required procedures, please refer to [Section 5](#).

Screening Phase:

- Begins by establishing the subject's initial eligibility and signing of the informed consent form (ICF).
- Subject is assessed for complete study eligibility within the required timeframe found in Table 7.1-1.
- A pregnancy test for WOCBP should be documented within 24 hours prior to the start of the first dose of study medication.
- All subjects must have at least 2 distinct lesions as documented by a complete physical examination or imaging studies within 4 weeks prior to randomization. Imaging studies must include a CT scan of the involved disease sites and all known sites of resected disease and brain magnetic resonance (MRI) or CT (brain CT allowable if MRI is contraindicated or if there is no known history of resected brain lesions).

Treatment Phase:

- Following confirmation of the subject's eligibility, the randomization call to the Moffitt Cancer Center Biostatistics Core can be made. The subject is randomly assigned to the Arm A (nivolumab + ipilimumab) or Arm B (nivolumab + ipilimumab + SBRT).
- Within 2 weeks from randomization the subject must receive the first dose of study medication (Day 1 of Week 1)
- On-study laboratory assessments should be drawn within 72 hours prior to dosing
- Adverse event assessments for grade ≥ 2 toxicities should be documented at each clinic visit and WOCBP must have a pregnancy test every four weeks +/- 1 week.
- Treated subjects will be evaluated for recurrence every 12 weeks +/- 7 days
- Patient Reported Outcome (PRO) instruments must be completed after randomization, prior to the dose of study therapy.

Follow-up Phase:

- Begins after 1 year of treatment or when the decision is made to discontinue a subject from study therapy.
- Patient may continue on the study drug under the treatment protocol indefinitely during the follow-up phase.
- After completion of the first two follow-up visits, subjects will be followed every 3 months for survival.

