5.5 SBRT and Drug Dosing Schedule

5.5.1 Dosing Schedule

First dose must be administered within 2 weeks following randomization. Subjects may be dosed up to ± 2 days before or after the scheduled date if necessary.

The Dosing schedule is described in [Table 5.5-1](#) and [Table 5.5-2](#).

	Week 1	Week 2	Week 3	Week 5
Arm A: Nivolumab+ Ipilimumab	240 mg Nivolumab + 1 mg/kg Ipilimumab		240 mg Nivolumab	240 mg Nivolumab
	Week 7			
	240 mg Nivolumab Every 2 weeks + 1 mg/kg Ipilimumab Every 6 weeks until progression or unacceptable toxicity			

	Week 1	Week 2	Week 3	Week 5
Arm A: Nivolumab+ Ipilimumab+ SBRT	240 mg Nivolumab + 1 mg/kg Ipilimumab	24Gy/3fx SBRT (may be completed by Week 3)	240 mg Nivolumab	240 mg Nivolumab
	Week 7			
	240 mg Nivolumab Every 2 weeks + 1 mg/kg Ipilimumab Every 6 weeks until progression or unacceptable toxicity			

If a subject cannot receive a dose within 2 days of its scheduled administration date, the dose should be completely omitted. When the subject is able to re-initiate treatment, dosing should resume at the time of the next scheduled dose. Missed doses will not be replaced.

5.5.2 *Antiemetic Premedications*

Antiemetic premedications should not be routinely administered prior to dosing of drugs. See [Section 5.5.8](#) for premedication recommendations following a nivolumab or ipilimumab related infusion reaction.

5.5.3 *Dose Modifications*

There will be no dose modifications permitted. Dose reductions or dose escalations are not permitted.

5.5.4 *Management Algorithms for Immuno-Oncology Agents*

Immuno-oncology (I-O) agents are associated with adverse events that can differ in severity and duration than adverse events caused by other therapeutic classes. Nivolumab and ipilimumab are considered immuno-oncology agents in this protocol. Management algorithms have been developed to assist investigators in assessing and managing the following groups of adverse events: Gastrointestinal, Renal, Pulmonary, Hepatic, Endocrinopathies, Skin, and Neurological. (Appendix 4)

Early recognition and intervention are recommended according to the management algorithms; and in addition include ophthalmologic evaluations for any visual symptoms in order to evaluate for nivolumab or ipilimumab related uveitis.

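### Section 1.4.8 caps ipilimumab at 4 doses, but the synopsis and dosing tables give it every 6 weeks with no cap: 4 against up to 9 scheduled doses by Week 49, in both arms

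*Combined protocol and SAP*

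**What the plan says.** Section 1.4.8 reviews toxicity and discontinuation in earlier ipilimumab and combination trials. It then draws a conclusion for the present study: to limit toxicity that would lead to stopping study drug, "ipilimumab is limited to 4 doses while nivolumab will continued until progression".

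The sections that set out treatment do not contain that limit:

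- The synopsis, under Treatment Arms, uses the same wording for Arm A and Arm B: "Ipilimumab 1 mg/kg IV over 30 min q6 weeks until progression or unacceptable toxicity". Its opening statement on investigational products says "Treat subjects until disease progression, unacceptable toxicity or subject withdrawal of consent", with no separate rule for ipilimumab.
- Section 1.4.7 gives the dose and interval without a number of doses: "we will utilize ipilimumab at 1 mg/kg Q6W in combination with nivolumab in this trial".
- Section 4.1 says "The subjects will be treated in both arms until disease progression, unacceptable toxicity, or subject withdrawal of consent". For the period after one year of treatment it adds "Patient may continue on the study drug under the treatment protocol indefinitely during the follow-up phase".
- Both dosing tables in Section 5.5.1 show ipilimumab at Week 1, and from Week 7 onward "1 mg/kg Ipilimumab Every 6 weeks until progression or unacceptable toxicity".

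The second of those tables includes SBRT in Week 2 but is headed Arm A. SBRT belongs to Arm B in the synopsis and in Sections 4.1 and 5.4.

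**The concern.** How long an investigational drug is given is an operative rule, and a reader of this protocol cannot tell which rule applies. Sites working from different sections would give different regimens in both arms. A site that follows the dosing tables leaves unapplied a limit that Section 1.4.8 introduces for safety. A site that follows Section 1.4.8 departs from the dosing tables. Section 10.1.4 requires conduct exactly as the protocol describes, which is not possible for ipilimumab after the fourth dose.

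The matter also reaches nivolumab. Section 5.5.5 delays all study drugs for a qualifying drug-related event, whichever drug it is attributed to. An event caused by a fifth or later ipilimumab dose would therefore interrupt both agents.

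For interpretation, both arms are compared with a 17% historical response rate as well as with each other. If the duration of one component is unsettled, the results do not belong to one defined regimen.

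**Working it through.** No sample size, power or error rate depends on this point. The check is a comparison of the two rules and a count of scheduled doses.

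**Inputs**

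- First ipilimumab dose in Week 1, second in Week 7, then every 6 weeks (Section 5.5.1 tables).
- Cap of 4 doses (Section 1.4.8), or no cap (synopsis, Section 5.5.1).
- Last on-treatment visit tabulated: Week 49 (Table 7.1-6).
- Dose 1 mg/kg, no dose changes allowed, missed doses not replaced (Sections 5.5.1 and 5.5.3).

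**Count**

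Dose number k falls in Week 1 + 6(k − 1). The fourth dose is in Week 1 + 6 × 3 = Week 19, and the fifth would be in Week 25. With no cap, the number of doses scheduled by Week w is the whole part of (w − 1)/6, plus 1. For w = 49 this is 48/6 + 1 = 9, namely Weeks 1, 7, 13, 19, 25, 31, 37, 43 and 49.

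| Through week | No cap | Cap of 4 | Ratio |
|---|---|---|---|
| 24 | 4 | 4 | 1.00 |
| 25 | 5 | 4 | 1.25 |
| 43 to 48 | 8 | 4 | 2.00 |
| 49 to 52 | 9 | 4 | 2.25 |
| 104 | 18 | 4 | 4.50 |

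At 1 mg/kg per dose, the cumulative scheduled amount by Week 52 is 9 mg/kg against 4 mg/kg. The difference is 9 − 4 = 5 doses in the first year. Under the uncapped rule it keeps growing until progression or unacceptable toxicity.

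**Which outcomes can be affected**

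Tumour assessments are every 12 weeks from first dose (Section 7.4), so they fall nominally at the start of Weeks 13, 25 and 37. The first comes before the rules part. The second coincides with the visit at which a fifth dose would be given, so that dose cannot have contributed to it. By the third, up to two further doses (Weeks 25 and 31) could have been given. A response seen at 12 weeks and confirmed at 24 weeks is therefore the same under either rule. Later responses, PFS, OS and cumulative toxicity are not protected in this way.

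**The case against.** The cap appears once, in the closing sentence of a background section. The sections that direct treatment (synopsis, 4.1 and 5.5.1) agree with one another, and the study-treatment row of every on-treatment visit table refers sites to Section 5.5. Most sites would probably follow those tables, and nothing in the documents shows that dosing has actually differed. This lowers the likelihood of mixed dosing. It does not settle what was intended, because Section 1.4.8 gives an explicit toxicity reason, and if every site follows the tables that safeguard is simply not applied.

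The ratio above 2 depends on the Week 49 dose. The synopsis describes treatment-period assessments as running through Week 45, and on that window the count is 8 against 4, exactly twofold. The figures are also maxima for a patient who neither stops nor misses a dose. Patients who stop before Week 25 are unaffected, and the average difference cannot be computed from the documents. These points stand and limit the size of the problem.

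Both arms carry identical wording, so the ambiguity does not systematically favour A or B. That also stands. Two weaker risks remain. Randomisation is stratified by prior immunotherapy only, so a difference between sites could be unevenly spread across arms by chance. The study is also unblinded, so an investigator could resolve the ambiguity differently by arm.

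The Arm A heading on the SBRT table is editorial. Its row names SBRT, and misdosing on that account is unlikely.

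**Conclusion.** The concern holds. The current text contains two rules for the duration of ipilimumab, both presented as this trial's own, and they cannot both be followed beyond Week 24. For a patient on treatment through Week 49 without missed doses, they give 4 and 9 scheduled doses (ratio 2.25). The gap is smaller for anyone who stops earlier or misses doses, and it is nil for anyone who stops before Week 25. Early confirmed responses are not affected. Cumulative toxicity, discontinuation, later responses, PFS and OS could be. There is no inherent bias between arms, but the regimen under study is not uniquely defined. Which duration is intended is a clinical matter for the sponsor, and this review takes no position on it.

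**What to change.** - Have the sponsor confirm the intended ipilimumab duration and state it in the same terms in the synopsis, Sections 1.4.7, 1.4.8 and 4.1, and both tables of Section 5.5.1.
- Correct the arm heading on the SBRT dosing table.
- Notify sites of the clarification.
- If patients have already been treated under both readings, report the number of ipilimumab doses received by arm, so that the toxicity and late efficacy results can be read against actual exposure.

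The cost is a clarifying amendment and a site notice. Sample size, decision rules and planned tests do not change. The only possible analysis work is one descriptive exposure table, needed only if dosing has in fact differed.
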